#### **Statistical Analysis Plan**

**Overall.** Based on preliminary data, we anticipate minimal attrition ( $\leq 5\%$ ) during the first two assessment sessions (pre-delivery), and up to 33% attrition postpartum across both groups in the worst-case scenario. All participants with data available for a given study phase (pre- or postpartum) will be included in the primary analyses. Before conducting hypothesis tests, we will screen all variables at all time points for out-of-range values, outliers, and data inconsistencies. Means, standard deviations, interquartile range, minima, and maxima for continuous variables and proportions for categorical variables will be reported.

Following CONSORT guidelines, the primary analyses for all aims will follow an intention-to-treat (ITT) approach, including all randomized participants regardless of treatment adherence or dropout. If significant imbalances in baseline covariates (e.g., maternal age, BMI, birth order, infant sex) are observed despite randomization, these variables will be included as covariates in the models. Additional exploratory models will examine relevant biological factors, such as maternal BMI, fetal/infant sex, maternal age, infant gestational age at birth, and birthweight corrected for birth age, as potential covariates.

**Aim 1.** Reduce women's distress during pregnancy. We hypothesize that PREPP will be associated with: (A) Diminished depressive symptoms using interviewer-rated and self-report questionnaires; (B) Improved perception of sleep quality relative to objective changes in sleep duration (per self report and actigraphy).

**Analysis for Aim 1A:** For depressive symptom outcomes (HRSD, PHQ-9, HRSA, PSQI, EPDS), we will fit linear mixed-effects models with fixed effects for Treatment (PREPP vs. ETau), Time (2nd and 3rd assessments), and birth order, along with subject-specific random intercepts. For EPDS, we will adjust for the screening score and test a Treatment  $\times$  Screening Score interaction as a secondary analysis. Additional moderators will also be tested.

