**Analysis for Aim 1B:** Two ActiGraph-derived measures, total sleep time (TSTact) and sleep efficiency (SEact), will serve as outcomes in separate mixed-effects models with fixed effects for time and day (within the ActiGraph epoch) and subject-specific random intercepts, assuming an AR(1) correlation structure. We will assess whether adjustment for weekday/weekend is warranted. Subject-specific means of these measures will be used as predictors of their subjective

counterparts (TSTact, SEact) in additional mixed models testing for treatment group differences in the association between objective and subjective sleep measures. Moderation by trauma history and attachment will be explored.

**Aim 2. Determine the maintenance of improved maternal mood and differences in infant behavior.** We hypothesize that PREPP will be associated with: (A) Lower rates of PPD and distress, including poor sleep efficiency, assessed by interviewer-rated and self-report questionnaires as well as sleep actigraphy. (B) Less infant fuss/cry behavior and longer nocturnal sleep bouts based on maternal report and actigraphy.

**Analysis for Aim 2A:** Separate linear mixed-effects models will be used for each maternal mood outcome (PHQ-9, HRSD, EPDS, HRSA, PSQI) and ActiGraph-derived sleep measures. Models will include Treatment, Time (6, 12, and 16 weeks postpartum), and their interaction, with baseline (pregnancy) values as covariates. Subject-specific random intercepts will be included. The primary parameter of interest is the Treatment  $\times$  Time interaction; if non-significant, the main effect of Treatment will be tested. PPD diagnosis will be modeled using mixed-effects logistic regression with analogous fixed effects.

For infant outcomes (6 and 16 weeks), linear mixed-effects models will assess Treatment effects without Time  $\times$  Treatment interaction. Sleep data will be processed as in Aim 1B. Covariates include time-varying factors such as weaning, solid food introduction, maternal return to work, and social support. Moderators (infant sex, trauma history, attachment) will also be assessed.

**Analysis for Aim 2B:** Infant sleep and cry behavior at 6 and 16 weeks will be compared using mixed-effects models with Treatment, Time, and their interaction as fixed effects. Covariates and secondary analyses will be same as those in Aim 2A.

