**Power analysis** We adjusted for multiple comparisons (five primary outcomes across Aims 1 and 2) using Bonferroni correction, resulting in a significance threshold of 0.01. For Aim 1, with  $N = 214$  and an assumed 5% attrition, our mixed-effects model analysis is powered to detect a minimum effect size of  $d = 0.48$  (assuming within-subject correlation  $r = 0.2$ ). Prior research has shown larger effects (e.g.,  $d = 0.85$  for EPDS in mindfulness-based therapy), indicating our design has ample power. For Aim 2, assuming 33% attrition and five primary outcomes, power calculations show that  $N = 107$  per group is sufficient to detect interactions as small as  $d = 0.087$  with 80% power at a Bonferroni-adjusted  $\alpha = 0.01$ . Our preliminary data support this assumption. For Aim 3, based on tabulated recommendations 184 for sample sizes needed to test mediation effects, with  $N=142$  completers (assuming 33% attrition for assessments), we have more than 80% power to detect a significant mediation effect with moderate effect sizes ( $d=0.54$ ,

$r=0.26$  of both paths (i.e. the paths from treatment to the mediator(s) and the mediator(s) to outcomes). Since the full sample ( $N = 214$ ) will be used in mediation models, the actual power will exceed this estimate.

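### Single-step Bonferroni at 0.01 is valid, but Holm's step-down procedure keeps the same 0.05 family-wise bound and has more power when more than one primary outcome responds

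*Combined protocol and SAP*

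**What the plan says.** The only multiplicity rule is in the Power analysis paragraph of the Statistical Analysis Plan: "We adjusted for multiple comparisons (five primary outcomes across Aims 1 and 2) using Bonferroni correction, resulting in a significance threshold of 0.01". The same threshold carries the Aim 2 power statement, which is made "assuming 33% attrition and five primary outcomes" and "with 80% power at a Bonferroni-adjusted" level of 0.01. The Aim 1 statement gives N = 214, "and an assumed 5% attrition" and a detectable d = 0.48, "assuming within-subject correlation" of 0.2.

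The analysis sections for Aims 1 and 2 give no decision rule of their own, and no step-down, hierarchical or gatekeeping procedure appears anywhere. The five primary outcomes are not listed as such. The only set of five that the plan names is in the Aim 1A analysis ("For depressive symptom outcomes (HRSD, PHQ-9, HRSA, PSQI, EPDS") and again in the Aim 2A analysis ("Separate linear mixed-effects models will be used for each maternal mood outcome (PHQ-9, HRSD, EPDS, HRSA, PSQI"). Aim 2A tests the Treatment × Time interaction for each outcome and goes on to the treatment main effect if the interaction is not significant.

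**The concern.** Under the stated rule each primary outcome must reach p ≤ 0.01, however many of the others have already succeeded. Holm orders the five p-values and compares them in turn with 0.05/5, 0.05/4, 0.05/3, 0.05/2 and 0.05/1, stopping at the first failure. Its first step is the Bonferroni test, so whatever Bonferroni rejects Holm also rejects. It needs no assumption about correlation.

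The two rules differ only after one outcome has been rejected. If the primaries are the five mood and sleep scales, they measure related aspects of maternal distress, and an effective intervention could well move several of them. In that setting the fixed threshold makes a true effect on a second or later scale more likely to be missed than it need be.

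**Working it through.** **Inputs from the plan.** Five primary outcomes; per-test level 0.01; N = 214, or 107 per group; 5% attrition for Aim 1; d = 0.48; within-subject r = 0.2. Power of 80% is stated for Aim 2 and assumed here for Aim 1.

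**Assumptions not in the documents.** Two-sided tests. Equal correlation between the five test statistics, set to 0.3, 0.5 and 0.7.

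**The plan's own figures.**
- Level: 0.05/5 = 0.01, exact.
- Per group after attrition: 107 × 0.95 = 101.65.
- Detectable effect for a single-visit contrast: d = (z₀.₉₉₅ + z₀.₈₀) × √(2/n) = (2.576 + 0.842) × √(2/101.65) = 3.417 × 0.1403 = 0.479.
- Power at d = 0.48: the mean of the z-statistic is 0.48 × √(101.65/2) = 3.422, and Φ(3.422 − 2.576) = 80.1%.

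So d = 0.48 reproduces as a two-sided, single-visit comparison. The stated r = 0.2 is not needed to reach it.

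**Holm against Bonferroni.** Five correlated normal z-statistics were simulated, 300,000 replicates per setting, with mean 3.422 for each real effect and 0 otherwise. Power is averaged over the real effects. Ranges run over correlations 0.3 to 0.7.

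| Real effects at d = 0.48 | Bonferroni, per outcome | Holm, per outcome |
|---|---|---|
| Five | 80% | 87-89% |
| Three | 80% | 83-84% |
| Two | 80% | about 82% |
| One | 80% | 80% (gain of 0.1 point or less) |

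- All five significant when all five are real: 44/51/59% under Bonferroni and 72/75/79% under Holm, at correlations 0.3/0.5/0.7.
- At least one significant when all five are real: 99/98/95%, identical under both rules, because Holm's first step is the Bonferroni test.
- Per-outcome gain by correlation, all five real: Holm gives 90.6% at correlation 0 and 87.2% at 0.7, so closer correlation shrinks it.

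**Family-wise error.** With all nulls true the two rules agree (0.047/0.042/0.034). With three real effects and two true nulls, Bonferroni's actual error is 0.020/0.019/0.018 and Holm's is 0.040/0.036/0.032. The largest Holm value in any setting tried was 0.0475, at correlation 0 with one real effect. The bound is the same; the error actually incurred is higher under Holm when some nulls are true.

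**If two visits are averaged.** The Aim 1A model uses two assessments. With r = 0.2, the variance of a two-visit mean is (1 + 0.2)/2 = 0.6 of a single visit, so the mean z is 3.422/√0.6 = 4.418. Per-outcome power with all five real is then 97% under Bonferroni and 99% under Holm.

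**Aim 2, illustration only.** With 33% attrition, 107 × 0.67 = 71.69 per group. A simple single-visit contrast at d = 0.48 on all five goes from 62% to 71-72% per outcome. This is not the interaction that the plan powers at d = 0.087: the scale of that figure is not stated, I could not reproduce it, and nothing here depends on it.

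**The case against.** The strongest reply is that nothing in the plan is wrong. Bonferroni controls the error, 0.05/5 is exact, and the sample size was set at that level. This stands: the point concerns efficiency, and N does not change.

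Second, the largest gain is the most favourable case, with five real and equal effects at the 80% power point and a single visit. This also stands. With fewer real effects or averaged visits the gain is small, and at d = 0.85, the effect the plan cites from earlier research, power is about 100% under either rule.

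Third, a reader might take Holm as a free, one-sentence substitution. The documents do not support that, because Holm cannot be run on the text as it is:
- The family is not listed. If the five scales are tested in both Aims there are ten tests, and ten at 0.01 bound the family-wise error at 0.10. That gap affects Bonferroni equally, and Holm over five would not close it.
- In Aim 2A the move from interaction to main effect depends on non-significance. Under a fixed 0.01 that can be judged outcome by outcome. Under Holm the threshold depends on the other p-values, and replacing an interaction p-value with a main-effect p-value can change the ranks, so the rule becomes circular unless one p-value per outcome is fixed in advance.
- If the family spans both Aims, a pregnancy result with p above 0.01 cannot be concluded until the postpartum p-values are known.

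What survives is narrower. For any properly defined family, Holm rejects at least as much as Bonferroni at the same bound.

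**Conclusion.** The point holds as a cheap improvement. The gain is 7 to 9 points of power per outcome if all five effects are real at d = 0.48, 3 to 4 points if three are, 1 to 2 points if two are, and effectively none if one is. These sizes rest on two-sided single-visit contrasts, equal effects and assumed correlations of 0.3 to 0.7. That Holm never rejects less at the same 0.05 bound rests on none of these.

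A reader might infer that the plan's testing is invalid, that the trial is underpowered because of Bonferroni, or that true effects on later scales will be declared non-significant. None of these follows. Each outcome already has 80% power at the planned effect under the plan's rule, and the prospect of any positive primary result is the same under both.

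**What to change.** In the Statistical Analysis Plan, replace the fixed 0.01 threshold with Holm's step-down procedure at family-wise 0.05 over the five primary outcomes. In the same edit:

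1. List the five outcomes, with the Aim and time point to which each belongs.
2. Name the one pre-specified treatment p-value per outcome that enters Holm. For any Aim 2A outcome, say whether it is the interaction or the main-effect test.
3. Keep 0.01, Holm's first-step level, as the conservative level for the sample-size statement.

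Fix the change before any treatment comparison is seen; the documents do not say whether that point has passed.

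The cost is a few sentences and no participants. There are three downsides to accept and state. Intervals kept at the Bonferroni level may include zero for an outcome that Holm rejects. Actual family-wise error rises, within 0.05, when some nulls are true. If the family spans both Aims, Aim 1 conclusions at thresholds above 0.01 must wait for the postpartum results.

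### The 0.01 threshold is set for five unnamed primary outcomes, but the only matching five scales are tested in both Aim 1A and Aim 2A, so the guaranteed family-wise bound is 10%, not 5%

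*Combined protocol and SAP*

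**What the plan says.** The multiplicity rule appears only in the Power analysis paragraph of the Statistical Analysis Plan: "We adjusted for multiple comparisons (five primary outcomes across Aims 1 and 2) using Bonferroni correction, resulting in a significance threshold of 0.01". The five outcomes are not listed there or labelled elsewhere.

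Two analysis paragraphs list the same five scales:

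- Analysis for Aim 1A (pregnancy): "For depressive symptom outcomes (HRSD, PHQ-9, HRSA, PSQI, EPDS), we will fit linear mixed-effects models". The models carry a Treatment term and a Time term for the second and third assessments, so each scale has one treatment test.
- Analysis for Aim 2A (6, 12 and 16 weeks postpartum): "Separate linear mixed-effects models will be used for each maternal mood outcome (PHQ-9, HRSD, EPDS, HRSA, PSQI) and ActiGraph-derived sleep measures". Here the Treatment-by-Time interaction is the main parameter, and "if non-significant, the main effect of Treatment will be tested". Aim 2A also adds a binary outcome: "PPD diagnosis will be modeled using mixed-effects logistic regression with analogous fixed effects".

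The power statement for the second aim begins "For Aim 2, assuming 33% attrition and five primary outcomes" and again uses 0.01. The plan gives no testing order, gatekeeping rule or alpha split between the aims, and no level for the fallback main-effect test.

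**The concern.** A Bonferroni divisor has to count the tests in the family. Five is the number of scales. If these scales are the primaries, the family that the plan describes as spanning both aims contains ten treatment tests, before any second test in Aim 2A.

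The stake is how a positive result is read. A single scale crossing 0.01 in one aim would be reported as significant after correction across Aims 1 and 2. The reader would take the chance of any false positive in that family to be at most 5%, which the plan does not guarantee.

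**Working it through.** **Inputs from the Statistical Analysis Plan.** Threshold 0.01 for five outcomes; five scales in Aim 1A and the same five in Aim 2A; N = 214 with 5% attrition in Aim 1 ("and an assumed 5% attrition, our mixed-effects model analysis is powered to detect a minimum effect size of" 0.48); 107 per group in Aim 2, "with 80% power at a Bonferroni-adjusted" alpha of 0.01. Assumed: 1:1 allocation in Aim 1, two-sided tests, and 80% power for Aim 1, which the plan states only for Aim 2.

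**Step 1: the plan's threshold.** 0.05/5 = 0.01. It reproduces exactly. The overall 0.05 is implied, since 5 × 0.01 = 0.05.

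**Step 2: is Aim 1 also planned at 0.01?** Per-arm n = 214 × 0.95/2 = 101.65, and sqrt(2/101.65) = 0.1403. Detectable d = (z for alpha/2 + z for 80% power) × 0.1403:

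- alpha 0.01: (2.576 + 0.842) × 0.1403 = 0.479, which matches 0.48
- alpha 0.05: (1.960 + 0.842) × 0.1403 = 0.393, which does not

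So both aims are planned at 0.01. If the Aim 2 power statement means five outcomes in that aim alone, it uses the whole 5 × 0.01 = 0.05. One Aim 1 test then takes the total to 0.06, and five take it to 0.10.

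**Step 3: family-wise error for ten tests at 0.01.**

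- Bound: 10 × 0.01 = 0.10
- If independent: 1 − 0.99^10 = 0.096
- For comparison, five tests: bound 0.05; if independent, 1 − 0.99^5 = 0.049

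**Step 4: correlated tests.** The documents give no correlations, so the range is shown. Ten normal test statistics were simulated (1,000,000 draws), equally correlated within an aim, with a between-aim correlation of 0 to 0.5 for the same scale.

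| Correlation among scales | Family-wise error, ten tests at 0.01 |
|---|---|
| 0.3 | 8.7–9.2% |
| 0.5 | 7.8–8.3% |
| 0.7 | 6.4–6.8% |
| 0.8 | 5.5–5.9% |
| 0.9 | 4.4–4.6% |

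**Step 5: Aim 2A alone.** Under the null, a scale yields a false positive if the interaction is significant or, failing that, the main effect is. If both are tested at 0.01, the bound per scale is 0.02 (1 − 0.99^2 = 0.0199 if independent). Over five scales the bound is 0.10, or 0.096 if independent, within this one aim.

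**Step 6: effect of correcting the divisor.** 0.05/10 = 0.005.

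- Aim 1 detectable d: (2.807 + 0.842) × 0.1403 = 0.512
- Power at d = 0.48: 80.1% at 0.01, 73.1% at 0.005
- N to keep 80% power at d = 0.48 with 5% attrition: 215 at 0.01 (102 per arm), 245 at 0.005 (116 per arm)

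The 0.48 reproduces with one measurement per woman. Averaging two assessments at the plan's r = 0.2 multiplies the variance by (1 + 0.2)/2 = 0.6. The detectable d is then 0.371 at 0.01 and 0.396 at 0.005, so the real cost may be smaller.

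**The case against.** **The five are not identified as these scales.** This stands. Neither analysis paragraph calls them primary, and Aims 1 and 2 also cover actigraphy, PPD diagnosis and infant sleep and crying. Five tests divided between the aims would make 0.01 the right divisor, apart from the fallback step. The inference is still strong, because the stated count is five and exactly the same five scales appear in both aims. If another set was meant, the plan does not show which tests the threshold covers, and that too needs correcting.

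**Each aim could be its own family.** The aims ask different questions, and 5 × 0.01 = 0.05 would then hold for Aim 1A. But the Power analysis paragraph describes one family spanning both aims, and Step 5 shows that the second test in Aim 2A would breach a per-aim 5% bound as well.

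**Bonferroni is conservative with correlated scales.** This stands in part. Several of the scales measure depressive symptoms, so the actual level is probably below 9.6%. It falls under 5% only near a correlation of 0.9 across all five, which is unlikely for a set that also includes anxiety and sleep quality.

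**Stronger readings that the documents do not support.** A reader might call this an arithmetic error; the division is right, and the fault lies in how the family is defined. A reader might also add the five fallback tests and report fifteen tests (bound 15%, or 14.0% if independent). That requires a level for the fallback test and its relation to the interaction test, and the plan states neither. Nor does the problem show that the interaction should give way to a single Treatment contrast: the plan makes the interaction its main parameter for Aim 2A and bases the Aim 2 power figure on it.

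**Conclusion.** The concern holds as a gap between the control that the plan claims and what its tests deliver. If the five primaries are the five scales listed in both aims, ten treatment tests share a divisor of five. The guaranteed family-wise bound is then 10% (9.6% if independent), against an implied 5%. This is a failure of the guarantee, not a demonstrated error rate: under the assumed correlations of 0.3 to 0.8 the level is about 5.5% to 9.2%, and at 0.9 it is below 5%.

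Two parts do not depend on identifying the five: the plan does not say which tests 0.01 covers, and the two-stage test in Aim 2A carries no stated adjustment. This should be settled in the SAP, but it does not undermine the design.

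**What to change.** 1. Name the primary tests as scale-by-aim pairs, and state the overall alpha and the family.
2. Control the family actually tested: 0.05/10 = 0.005 per test, Holm over the ten, or a prespecified order between the aims with a stated rule for passing alpha. If separate families per aim are intended, say so and drop the claim of control across both.
3. In Aim 2A, make the interaction and the fallback main effect share one alpha per scale, for example by splitting it or by a single joint test of Treatment and Treatment by Time. Either keeps the interaction in the analysis.
4. State that actigraphy and PPD diagnosis are outside the family, if that is intended.
5. Restate the detectable effects. At 0.005, Aim 1 becomes about 0.51 on the formula that reproduces 0.48. The Aim 2 interaction figure of 0.087 must also be recomputed, for the new threshold and for whatever form item 3 takes; the plan does not give the correlation needed to do so here.

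The cost is SAP wording and somewhat less favourable stated power: at d = 0.48, Aim 1 falls from about 80% to 73%. The restated 0.51 is still well below the 0.85 that the plan cites from prior research. No new participants are needed if that loss is accepted; holding 80% power at d = 0.48 would take 245 rather than 215.

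### Aim 2's detectable interaction of d = 0.087 cannot be a standardised difference at this sample size, and the plan gives no contrast, time coding, time unit or correlation from which to recover its scale

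*Combined protocol and SAP*

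**What the plan says.** The power analysis at the end of the Statistical Analysis Plan divides alpha by five primary outcomes, giving 0.01. It reports three effect sizes.

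- **Aim 1** (N = 214, 5% attrition, within-subject correlation 0.2): "our mixed-effects model analysis is powered to detect a minimum effect size of" d = 0.48.
- **Aim 2** (33% attrition, 80% power, alpha 0.01): 107 "per group is sufficient to detect interactions as small as" d = 0.087, followed by "Our preliminary data support this assumption".
- **Aim 3** (142 completers): d = 0.54, given alongside r = 0.26.

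For the maternal mood outcomes, the Analysis for Aim 2A says: "Models will include Treatment, Time (6, 12, and 16 weeks postpartum), and their interaction, with baseline (pregnancy) values as covariates". Treatment × Time is the primary parameter, and "if non-significant, the main effect of Treatment will be tested". The section does not say whether Time is a linear trend or a three-level factor. No SD, time unit or correlation is given for Aim 2.

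**The concern.** Aim 2 has the same alpha as Aim 1 and fewer women, and its target is an interaction, which usually needs a larger effect than a main effect. Yet its stated detectable effect is about one fifth of Aim 1's (0.48 / 0.087 = 5.5).

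The figure matters because Treatment × Time is Aim 2A's primary parameter and its result decides whether the main effect is tested. The aim is worded as "Determine the maintenance of improved maternal mood and differences in infant behavior". A reader who takes d = 0.087 at face value could treat a non-significant interaction as good evidence that the effect is constant from 6 to 16 weeks. The test that then follows, the Treatment main effect, has no stated detectable size for Aim 2.

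**Working it through.** **Inputs**

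- Completers per group: 107 × 0.67 = 71.69, about 72 (power analysis). The plan's own 142 completers give 71, with almost the same results.
- Alpha 0.01, taken as two-sided because the plan does not say; power 80%. K = 2.576 + 0.842 = 3.4175.
- Within-person correlation r for Aim 2: not stated, so 0 to 0.8 is assumed. The random-intercept model implies equal correlation between visits; equal variances are assumed.
- Visits at weeks 6, 12 and 16: Sxx = 28.44 + 0.44 + 21.78 = 50.67.

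**Step 1. What d means elsewhere in the paragraph**

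Aim 1: K × √(2/n) with n = 107 × 0.95 = 101.65 gives 0.479, the stated 0.48. This is a single-time group difference and does not use the stated r = 0.2. Averaging two assessments at r = 0.2 would give 0.479 × √(1.2/2) = 0.37. The match shows the scale of d but does not prove the method. Aim 3: 0.54 / √(0.54² + 4) = 0.261, the stated 0.26. Both figures behave as standardised differences.

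**Step 2. Trying to reproduce 0.087 on that scale (n = 71.69)**

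- Difference in 6-to-16-week change, 1 df: K × √[(2/n) × 2(1 − r)].
- Slope per visit (visits scored 0, 1, 2): K × √[(2/n) × (1 − r)/2].
- Time categorical, 2-df test, linear pattern over ten weeks: 10 × √[λ × 2(1 − r)/(n × Sxx)]. Here λ = 13.88 is the chi-square noncentrality for 80% power at alpha 0.01.
- Completers per group needed for a change of 0.087 SD: 4(1 − r) × (K/0.087)².

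| Assumed r | 0 | 0.2 | 0.5 | 0.8 |
|---|---|---|---|---|
| Change, 1 df (SD) | 0.81 | 0.72 | 0.57 | 0.36 |
| Linear pattern over 10 weeks, 2 df (SD) | 0.87 | 0.78 | 0.62 | 0.39 |
| Slope, SD per visit | 0.40 | 0.36 | 0.29 | 0.18 |
| Power if true change difference is 0.087 SD | 1.5% | 1.7% | 2.1% | 3.9% |
| Completers per group needed for 0.087 (change) | 6,172 | 4,938 | 3,086 | 1,234 |

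Solving for the r that gives 0.087:

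- change: r = 1 − n × 0.087²/(4K²) = 0.988;
- per-visit slope: r = 1 − n × 0.087²/K² = 0.954.

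**Step 3. Other scales on which 0.087 might have been computed**

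- SD per week: K × √[(2/n) × (1 − r)/50.67] = 0.080 at r = 0 and 0.072 at r = 0.2, so 0.087 is close. Over ten weeks it is 0.87 SD.
- Cohen's f, 2-df interaction, N = 143: 80% power needs r of about 0.77. For a linear pattern, f is the ten-week difference times √(50.67/12)/10 = 0.2055, so 0.087 / 0.2055 = 0.42 SD.
- f-squared, 1 df, N = 142: power 81.5%, close to the stated 80%. Here 2 × √0.087 = 0.59 is in SDs of the analysed variable. If that is a change score, multiply by √[2(1 − r)]: 0.83, 0.75, 0.59 or 0.37 outcome SD at r = 0, 0.2, 0.5 or 0.8.

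**Step 4. The fallback test**

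Treatment effect averaged over three visits, unadjusted: K × √[(2/n) × (1 + 2r)/3] = 0.33, 0.39, 0.47 or 0.53 SD at r = 0, 0.2, 0.5 or 0.8.

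**The case against.** The strongest reply is that 0.087 was computed correctly on a scale that was then mislabelled. This stands as a real possibility: f-squared at the plan's own 142 completers and alpha gives 81.5% power, and a weekly slope is also near. So the documents do not prove an arithmetic error. They do show that either the number or its label is wrong, and Step 3 shows that no candidate scale makes the effect small.

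A reader might infer that 0.57 SD, which the Aim 1 formula gives at 72 per group, is the true detectable interaction. It is not. It is a single-time group difference that contains no correlation, and it equals the change contrast only at r = 0.5.

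Attrition of 33% is a bound, described as "up to 33% attrition postpartum across both groups in the worst-case scenario", and "All participants with data available for a given study phase (pre- or postpartum) will be included in the primary analyses", so 72 per group may be pessimistic. With all 107 per group, the detectable change is still 0.66, 0.59, 0.47 or 0.30 SD at the same values of r, and 0.087 needs r = 0.983. The planned baseline covariate does not rescue the figure either: a term that is constant over time cancels out of the interaction.

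The upper limit of r = 0.8 is a choice. At r = 0.9 the detectable change is 0.26 SD, still about three times 0.087.

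Finally, the plan nowhere says that a null interaction will be read as proof of a constant effect. That is a risk of misreading the power statement, not a stated rule.

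**Conclusion.** The concern holds: d = 0.087 is undefined, is not reproducible from the stated inputs, and is not achievable as a standardised difference at any ordinary within-person correlation. Over r = 0 to 0.8, the design detects a difference in 6-to-16-week change of about 0.81 down to 0.36 SD (1 df), or 0.87 down to 0.39 SD for a linear pattern on a 2-df test. These figures assume two-sided alpha, equal correlation and variance across visits, and attrition as complete loss of follow-up. The r range is assumed, because the plan's only value, 0.2, belongs to Aim 1.

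A reader might go further and conclude that the sample size is wrong or that Aim 2 is underpowered. The documents do not support that: they state no expected size for the interaction against which to judge it.

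**What to change.** Re-derive the Aim 2 figure and restate it in outcome-SD units. Name the contrast, the coding of Time (1 df or 2 df), the time unit and the assumed within-person correlation, and say what the preliminary data contribute to those assumptions. For example: with about 72 completers per group, two-sided alpha 0.01 and 80% power, the detectable Treatment difference in 6-to-16-week change is __ SD, assuming r = __ and Time coded as __.

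If 0.087 is a weekly slope, Cohen's f or f-squared, label it so and give its outcome-SD equivalent at the assumed r. A fixed conversion of f-squared to d = 0.59 should not be used, and 0.57 should not be entered as the replacement.

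Add the detectable averaged Treatment effect for the fallback test: about 0.33 to 0.53 SD unadjusted for r = 0 to 0.8, or the baseline-adjusted value with its assumptions.

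The cost is one restated sentence and one added figure. The stated sensitivity will look less favourable. Models, alpha and sample size do not change.
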